#### 2 ELIGIBILITY ASSESSMENT AND ENROLLMENT

#### 2.1 ELIGIBILITY CRITERIA

- 2.1.1 Inclusion Criteria
- 2.1.1.1 Patients must have histologically or cytologically confirmed Smoldering Multiple Myeloma confirmed by the Principal Investigator in discussion with the Laboratory of Pathology, NCI or the Department of Laboratory Medicine, CC, as needed, and based on the International Myeloma Working Group Criteria[45]:
  - Serum M-protein ≥3 g/dl and/or bone marrow plasma cells ≥10 % and <60%
  - Absence of anemia: Hemoglobin >10 g/dl
  - Absence of renal failure: serum creatinine < 2.0 mg/dL
  - Absence of hypercalcemia: Ca <10.5 mg/dl
  - Absence of lytic bone lesion on X-ray, CT, or PET/CT and not more than 1 lesion on spinal MRI (NOTE: At the discretion of the investigator, PET/CT may replace MRI in patients who have a contraindication to MRI.)
  - Involved/un-involved light chain ratio must be < 100
- 2.1.1.2 Measurable disease within the past 4 weeks defined by any one of the following:
  - Serum monoclonal protein  $\geq 1.0 \text{ g/dl}$
  - Urine monoclonal protein >200 mg/24 hour
  - Serum immunoglobulin free light chain >10 mg/dL AND abnormal kappa/lambda ratio (reference 0.26-1.65)

**NOTE:** As of Amendment L (version date 05/17/2018), the primary endpoint is MRD(-) CR rate; therefore, per the discretion of the Principal Investigator, patients without measurable disease (e.g., M-spike <1) may also be enrolled. This is in line with the most recent IMWG MM response criteria.

- 2.1.1.3 Age ≥18 years. Because no dosing or adverse event data are currently available on the use of carfilzomib in combination with lenalidomide in patients <18 years of age, children are excluded from this study, but may be eligible for future pediatric trials.
- 2.1.1.4 ECOG performance status ≤2 (Karnofsky ≥60%, see APPENDIX A)
- 2.1.1.5 Patients must have normal organ and marrow function as defined below:
  - absolute neutrophil count (ANC) ≥1.0 K/uL
     NOTE: At the discretion of the investigator, patients with an ANC of 0.5 K/uL –
     <1.0 K/uL may also be enrolled if clinically appropriate (e.g., patients with a baseline neutropenia that is chronic and that does not cause complications).

  - platelets >75 K/uL
  - hemoglobin > 8 g/dL (transfusions are permissible)
  - total bilirubin ≤1.5 X institutional upper limit of normal
  - AST(SGOT)/ALT(SGPT) < 3.0 X institutional upper limit of normal (ULN)
  - Serum creatinine ≤1.5 X institutional ULN. If serum creatinine is above 1.5 X ULN, Creatinine Clearance (CrCl) or eGFR (estimated glomerular filtration rate)

Version Date: 01/01/2024

must be  $\geq 50$  ml/min.

- CrCl will be calculated by Cockcroft-Gault method. CrCl (calculated) = (140 Age) x Mass (in kilograms) x [0.85 if Female] 72 x Serum Creatinine (in mg/dL).
- eGFR will be calculated by either of the following well established formulas: modification of diet in renal disease (MDRD) or the chronic kidney disease (CKD)-epidemiology collaboration (EPI) (institutional standard) equations.
- CrCl may also be determined by measuring a 24 hour urine collection The measured CrCl must be > 50 ml/min.
- 2.1.1.6 In addition to having SMM, patients must also be classified as "high-risk SMM" per Mayo Clinic[12] or Spanish PETHEMA[13] criteria. NOTE: Criteria set forward by Rajkumar, Landgren, Mateos [14] may also be used to define high risk disease, namely clonal bone marrow plasma cells ≥10% and any one or more of the following:
  - Serum M protein  $\geq 30 \text{g/L}$
  - IgA SMM
  - Immunoparesis with reduction of 2 uninvolved immunoglobulin isotypes
  - Serum involved/uninvolved FLC ratio ≥8 (but <100)
  - Progressive increase in M protein level (evolving type of SMM; increase in serum M protein by ≥25% on 2 successive evaluations within a 6-month period)
  - Clonal BMPCs 50%-60%
  - Abnormal PC immunophenotype (≥95% of BMPCs are clonal) and reduction of ≥1 uninvolved immunoglobulin isotypes
  - t(4;14) or del(17p) or 1q gain
  - Increased circulating PCs
  - MRI with diffuse abnormalities or 1 focal lesion
  - PET-CT with focal lesion with increased uptake without underlying osteolytic bone destruction
- 2.1.1.7 All study participants must be registered into the mandatory REMS® program, and be willing and able to comply with the requirements of REMS®.
- 2.1.1.8 The effects of carfilzomib on the developing human fetus are unknown. The immunomodulatory agents used in this trial (i.e., lenalidomide) are known to be teratogenic. Women of child-bearing potential and men must agree to use adequate contraception. Females of childbearing potential (FCBP)† must have a negative serum or urine pregnancy test within 10-14 days and again within 24 hours prior to

† A female of childbearing potential is a sexually mature female who: 1) has not undergone a hysterectomy or bilateral oophorectomy; or 2) has not been naturally postmenopausal for at least 24 consecutive months (i.e., has had menses at any time in the preceding 24 consecutive months).

Version Date: 01/01/2024

prescribing lenalidomide for Cycle 1 (prescriptions must be filled within 7 days) and must either commit to continued abstinence from heterosexual intercourse or begin TWO acceptable methods of birth control, one highly effective method and one additional effective method AT THE SAME TIME, at least 28 days before she starts taking lenalidomide. FCBP must also agree to ongoing pregnancy testing. Men must agree to use a latex condom during sexual contact with a FCBP even if they have had a successful vasectomy. All patients must be counseled at a minimum of every 28 days about pregnancy precautions and risks of fetal exposure; see **APPENDIX B**: Requirements for REMS. Should a woman become pregnant or suspect she is pregnant while she or her partner is participating in this study, she should inform her treating physician immediately. In regard to carfilzomib, FCBP and their male partners must agree to use at least one method of effective contraception for at least 30 days after the last dose of carfilzomib and males must agree to use contraception and not to donate sperm for at least 90 days after the last dose of carfilzomib.

- 2.1.1.9 Ability of subject to understand and the willingness to sign a written informed consent document.
- 2.1.2 Exclusion Criteria
- 2.1.2.1 Patients who are receiving any other investigational agents.
- 2.1.2.2 Concurrent systemic treatment or prior therapy within 4 weeks for SMM. **NOTE:** Treatment with corticosteroids for other indications is permitted
- 2.1.2.3 Patients with a diagnosis of MM as defined by the 2014 IMWG diagnostic criteria[45]
- 2.1.2.4 Contraindication to any concomitant medication, including antivirals, anticoagulation prophylaxis, tumor lysis prophylaxis, or hydration given prior to therapy
- 2.1.2.5 History of allergic reactions attributed to compounds of similar chemical or biologic composition to carfilzomib or lenalidomide agents used in study, such as bortezomib or thalidomide, in addition to patients with known allergy to sulfobutyl ether β-cyclodextrin (Captisol®).
- 2.1.2.6 Uncontrolled hypertension or diabetes
- 2.1.2.7 Pregnant or lactating females. Pregnant women are excluded from this study. The effects of carfilzomib on a developing human fetus are unknown. Lenalidomide is teratogenic with unknown potential for abortifacient effects. Breastfeeding women and women planning on breastfeeding may not participate. No studies of carfilzomib have been conducted on breast feeding women and it is not known if it is excreted in milk. Because there is an unknown but potential risk for adverse events in nursing infants secondary to treatment of the mother with Carfilzomib/Lenalidomide, breastfeeding should be discontinued if the mother is treated with Carfilzomib/Lenalidomide.
- 2.1.2.8 Significant cardiovascular disease with NYHA Class II, III or IV symptoms, or hypertrophic cardiomegaly, or restrictive cardiomegaly, or myocardial infarction within 3 months prior to enrollment, or unstable angina, or unstable arrhythmia.
- 2.1.2.9 Active hepatitis B or C infection.

*Version Date:* 01/01/2024

2.1.2.10 Has refractory GI disease with refractory nausea/vomiting, inflammatory bowel disease, or bowel resection that would prevent absorption.

- 2.1.2.11 Significant neuropathy >Grade 2 at the time of first dose or within 14 days of enrollment.
- 2.1.2.12 Uncontrolled intercurrent illness including, but not limited to, ongoing or active infection, symptomatic congestive heart failure, unstable angina pectoris, cardiac arrhythmia, or psychiatric illness/social situations within 2 weeks that would limit compliance with study requirements.
- 2.1.2.13 History of other malignancy (apart from basal cell carcinoma of the skin, or in situ cervix carcinoma) except if the patient has been free of symptoms and without active therapy during at least 2 years or if, at the clinical discretion of the investigator, the risks of this study do not outweigh the potential benefits on a case to case basis.
- 2.1.2.14 Major surgery within 1 month prior to enrollment.

# 2.1.3 Recruitment Strategy

Participant sources will include NIH patient populations and outside physician referrals. Of note, our outside physician referral network has a high representation of minorities.

This protocol may also be abstracted into a plain language announcement and posted on NIH websites and on NIH social media platforms.

In addition, we will work with specialists from the NIH Clinical Center Office of Patient Recruitment to develop study-specific public service announcements (e.g., Twitter, Facebook, etc.) and informational fliers to be used for recruitment activities. All information to be posted or distributed publicly will be submitted to the IRB for review and approval in advance of use.

Investigators may also take part in online and in-person patient support groups and social media forums where patients gather for networking, general support and information about their disease. These groups and forums may also serve as indirect recruitment referral resources (e.g., investigators may provide information/links to publicly available resources for more information on clinical trials to which a patient may self-refer).

#### 2.2 SCREENING EVALUATION

2.2.1 Screening activities performed prior to obtaining informed consent

Minimal risk activities that may be performed before the subject has signed a consent include the following:

- Email, written, in person or telephone communications with prospective subjects
- Review of existing medical records to include H&P, laboratory studies, etc.
- Review of existing MRI, x-ray, or CT images
- Review of existing photographs or videos
- Review of existing pathology specimens/reports from a specimen obtained for diagnostic purposes

A waiver of consent for these activities has been requested in section 12.5.1.

Version Date: 01/01/2024

### 2.2.2 Screening activities performed after a consent for screening has been signed

The following activities will be performed only after the patient has signed the screening consent for this study or the consent for study 01C0129 (provided the procedure is permitted on that study) on which screening activities may also be performed. Assessments performed at outside facilities or on another NIH protocol within the timeframes below may also be used to determine eligibility once a patient has signed the consent.

A complete history and physical examination with documentation of measurable disease and assessment of performance status using the ECOG scale must be performed prior to study entry.

The following studies and laboratory tests will be completed 4 weeks prior to study entry, unless otherwise noted:

- CBC with differential and reticulocyte count
- Acute Care (sodium, potassium, chloride, CO2, glucose, BUN, creatinine), Mineral (serum calcium, phosphate, magnesium and albumin) and Hepatic (alkaline phosphatase, ALT, AST, total and direct bilirubin) Panels, and CrCl calculation
- Uric acid, LDH, and Beta-2 Microglobulin
- Serum protein electrophoresis (SPEP) and immunofixation to assess for presence and quantity of monoclonal protein (M-protein)
- Random urine sample for protein electrophoresis (UPEP) and immunofixation to assess for monoclonal protein in the urine (Bence-Jones proteinuria). Collect a 24 hour urine sample if necessary for confirmation of Smoldering Multiple Myeloma diagnosis [i.e. if patient's serum monoclonal protein is not measurable (< 1.0 g/dl)].
- Serum free light-chain studies
- Quantitative immunoglobulins
- Viral serologies: Hepatitis B surface antigen and Anti Hepatitis C (HCV) antibody. If Anti HCV is positive, will follow with HCV RNA PCR
- If the patient does not meet Mayo Clinic criteria or the criteria set forth by Rajkumar, Landgren, Mateos for high-risk SMM, but he/she has evidence of immunoparesis, the patient will have to undergo a bone marrow core biopsy and/or aspirate with flow cytometry to determine high-risk disease as defined by the PETHEMA criteria. If a bone marrow aspirate is done at screening, then the sample can be processed for baseline assays (see APPENDIX C: Bone Marrow Aspirate Collection, Sorting and Storage) to minimize the number of bone marrow biopsies
- Serum or urine pregnancy test in women of child-bearing potential.
- 12-lead EKG
- A skeletal survey of the axial and appendicular skeleton will be performed. (**NOTE:** A skeletal survey does not have to be repeated if performed at the NIH within 3 months of screening.)
- A spinal MRI (cervical/thoracic/lumbar) is required prior to study entry to exclude ≥ 2 lytic lesions; if patient has had an MRI performed at an outside facility, one performed at

Version Date: 01/01/2024

NIH is not required but may be performed for research purposes. (NOTE: At the discretion of the Principal Investigator, PET/CT may replace MRI in patients who have a contraindication to MRI.) (**NOTE:** An MRI does not have to be repeated if performed at the NIH within 3 months of screening.)

#### 2.3 PARTICIPANT REGISTRATION AND STATUS UPDATE PROCEDURES

Registration and status updates (e.g., when a participant is taken off protocol therapy and when a participant is taken off-study) will take place per CCR SOP ADCR-2, CCR Participant Registration & Status Updates found at:

https://ccrod.cancer.gov/confluence/pages/viewpage.action?pageId=73203825.

#### 2.3.1 Screen Failures

Screen failures are defined as participants who consent to participate in the clinical trial but are not subsequently assigned to the study intervention or entered in the study. A minimal set of screen failure information is required to ensure transparent reporting of screen failure participants, to meet the Consolidated Standards of Reporting Trials (CONSORT) publishing requirements and to respond to queries from regulatory authorities. Minimal information includes demography, screen failure details, eligibility criteria, and any serious adverse event (SAE).

Individuals who do not meet the criteria for participation in this trial (screen failure) will not be rescreened.

#### 2.4 Treatment Assignment and Randomization/Stratification Procedures

#### 2.4.1 Cohorts

Number	Name	Description
1	Multiple myeloma	Smoldering multiple myeloma patients with high-risk disease

#### 2.4.2 Arms

Designation	Name	Description
A	Experimental: Treatment (Carfilzomib, Revlimid and Dexamethasone)	Carfilzomib (IV, Days 1, 2, 8, 9, 15, and 16 of the 28-day cycle); Revlimid (PO, Days 1-21 of the 28-day cycle; exception: not given on cycle 1 day 1); and, Dexamethasone (PO or IV, Days 1, 2, 8, 9, 15, 16, 22, and 23 of the 28-day cycle; exception: not given on cycle 1 day 1)
		(NOTE: Closed upon activation of Amendment H version date 06/12/2017.)
В	Experimental: Treatment (Carfilzomib, Revlimid and Dexamethasone)	Carfilzomib (IV, Days 1, 2, 8, 9, 15, and 16 of the 28-day cycle); Revlimid (PO, Days 1-21 of the 28-day cycle); and, Dexamethasone (PO or IV, Days 1, 2, 8, 9, 15, 16, 22, and 23 of the 28-day cycle) (NOTE: Opened effective with Amendment H. version date 06/12/2017)

## 2.4.3 Treatment Assignment and Randomization/Stratification

Single arm/group assignment; open-label and non-randomized.

Version Date: 01/01/2024

#### 2.5 BASELINE EVALUATION

Research and clinical laboratory tests to be performed prior to starting therapy. Refer to Section 5 for details on biospecimen collection and correlative studies.

2.5.1 Echocardiogram, Pro Brain-type natriuretic peptide (BNP) PT, PTT, and Troponin

## 2.5.2 Bone Marrow

- Histopathological evaluation on bone marrow aspirate and biopsy
- Immunophenotyping of aberrant clonal plasma cells by multiparametric flow cytometry.
- Interphase FISH/cytogenetics (If previously done, repeat not necessary)
- CD 138+ fractions and CD 138- fractions cell sorting with subsequent correlatives on both fractions to be done in the [name] Lab.
- Proteasome activity and quantification (peripheral blood and bone marrow).
- Immunoglobulin heavy and/or light chain rearrangement.
- 2.5.3 Peripheral Blood, Urine, and Imaging
  - Peripheral blood and urine samples for storage and establishing a biobank. (See **APPENDIX D**APPENDIX D: Peripheral Blood and Urine Collection and Storage)
  - Subunit profiling and activity of circulating proteasomes by enzyme-like immunosorbent assay (optional).
  - Apoptosis assays to identify necrotic or late stage apoptotic cells.
  - Immunolocalization studies.
  - Peripheral blood flow cytometry assessing for circulating plasma cells under the direction of [name]
  - Peripheral blood will be assessed for immune cell populations including, but not limited to T cells (CD4 and CD8), LGL, and NK cells using flow cytometry.
  - FDG PET/CT scan within 4 weeks of study entry and prior to starting therapy. NOTE: See additional information in Section 5.1.3
  - Diffusion Weighted Whole Body (DW-MRI) (exception: patients with a contraindication or inability to perform due to administrative or logistical reasons
- 2.5.4 Questionnaires/Patient-Reported Outcomes (PROs)

**NOTE:** See Section 5

### **STUDY IMPLEMENTATION**

#### 3.1 STUDY DESIGN

Patients with high risk SMM will be enrolled on the pilot study and treated with 3-drug combination (Cycles 1-8 carfilzomib 20/36 mg/m², lenalidomide 25 mg, dexamethasone 20 mg cycles 1-4 and 10 mg cycles 5-8) followed by extended lenalidomide dosing.

All ongoing testing and procedures will take place per the Study Calendar, Section **3.4**. **NOTE:** Treatment is planned to be administered on an outpatient basis. At the investigator's discretion (e.g., for additional monitoring, patient social reasons, etc.), patients may be treated on an

Version Date: 01/01/2024

inpatient basis. Any cases of planned hospitalization are not considered reportable serious adverse events per Section 8.4.

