## 4.1.3 Clinical Monitoring

- a. Signs and symptoms indicative of TLS, such as fevers, chills/rigors, dyspnea, nausea, vomiting, muscle tetany, weakness, or cramping, seizures, and decreased urine output.
- b. Patients will be admitted to the inpatient hospital and observed while receiving Cycle 1 Days 1 and 2 of therapy.

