## 8.1.2 Serious Adverse Event (SAE)

An adverse event or suspected adverse reaction is considered serious if in the view of the investigator or the sponsor, it results in any of the following:

- Death,
- A life-threatening adverse event (see section **8.1.3**)
- Inpatient hospitalization or prolongation of existing hospitalization
  - A hospitalization/admission that is pre-planned (i.e., elective or scheduled surgery arranged prior to the start of the study), a planned hospitalization for pre-existing condition, or a procedure required by the protocol, without a serious deterioration in health, is not considered a serious adverse event.
  - A hospitalization/admission that is solely driven by non-medical reasons (e.g., hospitalization for patient or subject convenience) is not considered a serious adverse event.

*Version Date:* 01/01/2024

 Emergency room visits or stays in observation units that do not result in admission to the hospital would not be considered a serious adverse event. The reason for seeking medical care should be evaluated for meeting one of the other serious criteria.

- Persistent or significant incapacity or substantial disruption of the ability to conduct normal life functions.
- A congenital anomaly/birth defect
- Important medical events that may not result in death, be life-threatening, or require hospitalization may be considered a serious adverse drug experience when, based upon appropriate medical judgment, they may jeopardize the patient or subject and may require medical or surgical intervention to prevent one of the outcomes listed in this definition.

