# SAEs will be:

 Assessed for severity and relationship to study product and alternate etiology (if not related to study product) by a licensed study physician listed on the Form FDA 1572 as the site principal investigator or sub-investigator.

Version Date: 01/01/2024

• Recorded on the appropriate SAE report form, the medical record and captured in the clinical database.

• Followed through resolution by a licensed study physician listed on the Form FDA 1572 as the site principal investigator or sub-investigator.

For timeframe of recording adverse events, please refer to section **6.1**. All serious adverse events recorded from the time of first investigational product administration must be reported to the sponsor with the exception of any listed in section **8.4**.

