#### 8.4 WAIVER OF EXPEDITED REPORTING TO CCR

As death and hospitalization due to disease progression are part of the study objectives, and captured as an endpoint in this study, they will not be reported in expedited manner to the sponsor. However, if there is evidence suggesting a causal relationship between the study drug and the event, report the event in an expedited manner according to section **8.3**.

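### Section 3.1 exempts any planned hospitalization from SAE reporting on the authority of section 8.4, but 8.4 contains no such waiver and the planned-admission rule in 8.1.2 is narrower

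*Combined protocol and SAP*

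**What the plan says.** The note in section 3.1 has three parts. Treatment is planned as outpatient. Inpatient treatment is allowed: "At the investigator's discretion (e.g., for additional monitoring, patient social reasons, etc.), patients may be treated on an" inpatient basis. The note then ends: "Any cases of planned hospitalization are not considered reportable serious adverse events per Section 8.4".

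Section 8.4 begins: "As death and hospitalization due to disease progression are part of the study objectives, and captured as an endpoint in this study". It waives expedited reporting of those events and restores it where evidence points to a causal link with study drug. Planned hospitalization is not mentioned.

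Section 8.2 says that recorded SAEs "must be reported to the sponsor with the exception of any listed in section" 8.4. Section 8.3 also points to 8.4 for exceptions to expedited reporting.

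Section 8.1.2 lists as a criterion of seriousness: "Inpatient hospitalization or prolongation of existing hospitalization". Its carve-out covers admissions fixed before the study, planned admissions for a pre-existing condition, and procedures the protocol requires; such an admission, "without a serious deterioration in health, is not considered a serious adverse event". A second carve-out covers admissions made only for non-medical reasons.

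On the first two treatment days, section 4.1.3 states: "Patients will be admitted to the inpatient hospital and observed while receiving Cycle 1 Days 1 and 2 of therapy". Section 3.3.7.1 leaves in-hospital observation on the same days to the investigator.

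**The concern.** The sentence in 3.1 relies on a section that does not contain the rule, and its scope is wider than that of the section that does. Correcting the section number alone would not cure this, because *any* planned hospitalization would still be broader than 8.1.2.

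The gap matters for one kind of case. Section 3.1 offers additional monitoring as a reason for inpatient treatment. That reason can be medical and can arise on study, for instance when a patient is brought in for the next dose because of a toxicity at the last one. One investigator could cite 3.1 and not report the admission. Another could cite 8.1.2 and report it.

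Evaluating toxicity is a secondary objective (1.1.2), and section 10.2 sets out to characterize the regimen's safety fully. The participants have a condition for which the background section gives observation as the standard of care, so the frequency of serious events is a figure readers will look for.

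**Working it through.** There is no stated figure to reproduce, so the check is a comparison of the rules.

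**Step 1. Does 8.4 contain the waiver that 3.1 cites?** No. Its only subject is death and hospitalization due to progression. Sections 8.2 and 8.3 name no other list of exceptions, so the reporting rules give the 3.1 exemption no support.

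**Step 2. How do the scopes compare?**

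| Feature | 3.1 | 8.1.2 | 8.4 |
|---|---|---|---|
| Admissions covered | Any that are planned | Arranged before the study; for a pre-existing condition; for a protocol-required procedure; solely non-medical | Due to disease progression |
| Health-deterioration condition | None | Applies to the planned-admission carve-out | Not applicable |
| Exception for drug causality | None | Not addressed | Yes; waiver withdrawn |
| Prolonged stay | Not mentioned | Separate SAE criterion | Not mentioned |

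**Step 3. Run cases through the rules.**

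- *Admission for social reasons only.* Exempt under 3.1 and under the non-medical carve-out in 8.1.2. No conflict.
- *Admission for Cycle 1 Days 1 and 2.* If required, as 4.1.3 has it, the stay plausibly falls under the protocol-required carve-out, and 3.1 and 8.1.2 agree. If discretionary, as in 3.3.7.1, that carve-out is less certain.
- *On-study admission planned for medical monitoring after a toxicity.* Exempt on the words of 3.1. Under 8.1.2 it was not arranged before the study, is not for a pre-existing condition, is not clearly protocol-required and is not solely non-medical. It is not listed in 8.4. The rules conflict.
- *Planned stay prolonged by an event.* Section 3.1 is silent and 8.1.2 counts prolongation separately. The event remains an SAE unless a site lets 3.1 override 8.1.2.

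**Step 4. What is lost if a site follows 3.1?** Section 6.1 still requires adverse events to be documented from Day 1 to 30 days after the last dose, and 8.2 still collects severity, relationship, seriousness and outcome. An event that is life-threatening, or otherwise meets 8.1.2, stays an SAE. Only the SAE status that rests on hospitalization alone is exposed.

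**Step 5. Size.** The documents give no number of planned admissions and no rate of those prompted by toxicity. For scale only: with the planned 50 evaluable patients, one patient whose sole SAE went unclassified would move the proportion with any SAE by 1/50 = 2 percentage points. That is not an estimate of how many there are.

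**The case against.** The strongest reply is context. The sentence closes a note about giving treatment to inpatients, so its natural subject is a stay arranged to deliver a dose. Section 3.3.3.1 generally holds the relevant drug for non-hematologic toxicity of grade 3 or higher, so an admission to manage such an event is not plainly inpatient treatment. On this view the defect is a wrong section number and one loose word. This stands as an account of what was probably meant. It does not remove the case of a later dose given in hospital because of an earlier toxicity, which is inpatient treatment for monitoring and falls squarely within the words of 3.1.

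Three stronger readings might be inferred, and the documents do not support them.

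- *Every treated patient is affected, because 4.1.3 admits everyone.* Section 3.3.7.1 makes that stay optional. If it is mandatory, 8.1.2 plausibly exempts it anyway.
- *Events that arise in or prolong a planned stay are exempt.* Section 3.1 does not say so, and calling an admission non-serious does not exempt a separate event.
- *Toxicity data disappear, or a percentage of SAEs can be said to be missing.* The adverse-event record remains in force, and no rate can be derived from the documents.

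It is also fair that rewording 3.1 now changes little going forward. The footnotes to the study calendar (3.4) state that all participants had completed maintenance by 6 February 2023. This moves the practical remedy to the final safety report.

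**Conclusion.** The inconsistency is real and should be corrected. Section 3.1 states a safety-reporting exemption that its cited authority does not contain and that is wider than the governing definition in 8.1.2. The consequence is a possibility: an on-study admission planned for medical monitoring after a toxicity may have been left out of SAE classification and reporting. Any such error lowers the SAE count. The primary endpoint, the MRD-negative complete response rate, is not touched.

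This rests on two assumptions: that at least some sites or staff read 3.1 literally, and that some planned admissions were prompted by a toxicity without meeting another seriousness criterion. The documents neither confirm nor exclude either, so the number affected is unknown and may be zero.

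**What to change.** 1. In 3.1, delete the reference to 8.4 and restate the sentence as: *Admission solely to give or observe protocol treatment, not prompted by an adverse event, is not an SAE (see 8.1.2); any adverse event that prompts, occurs during or prolongs such a stay is assessed and reported under 8.1.2 to 8.3.*
2. Reconcile 3.3.7.1 with 4.1.3 on whether the Cycle 1 Days 1 and 2 stay is optional or required, since that decides whether it counts as protocol-required under 8.1.2. Which of the two applies is for the sponsor to settle.
3. As treatment is complete, check all past planned admissions against 8.1.2 before the final safety report, and state in the report how they were classified.

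The cost is one reworded sentence, one reconciliation and a limited review of admission records. The reported SAE count may rise slightly. No dose, schedule or endpoint changes.
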